of good outcomes for these recent trials in the IAT arms have varied widely (52-71%). The investigators believe that a primary factor explaining differences between studies is the portion of people with favorable CIS included in the studies. Interestingly the ratio between the rate of good outcomes in the treatment arm vs. the control arm (no IAT) has been stable across the different positive trials showing the effect of IAT at approximately 1.7 for all of these recent trials, similar to the PROACT II trial more than 15 years ago. [3]. The investigators believe the stagnation of this ratio at 1.7 is evidence that the selection criteria have not improved despite improvement in the rate of revascularization. Based on the existing data, the investigators would like to evaluate the merit of CIS as a primary tool for patient selection in IAT, hoping to prove that the rate of treated to untreated improvement is on the order of 6 to 7. We expect that if we select for patients with fCIS and obtain good revascularization to obtain around 80% GCO in the treated arm. We also expect successful revascularization to be futile for patients with pCIS.

E. The principal investigator believes that the CIS for each patient is determined genetically. In order to explore the genetic link to the CIS, this trial also aims to perform SNP-trait association analysis to identify the genetic loci linked to CIS and stroke outcome in patients suffering from AIS. *Dce1* has recently been found to be responsible for approximately 85% of the variation in collateral extent and it is likely that polymorphisms of *Dce1* are a major determinant of the wide variation in collateral scores in humans. If it is shown that *Dce1* is correlated to CIS and both are predictive outcomes for EVT, then this will further increase confidence in CIS as an assessment of collateral status, strengthen patient stratification of patients to define course of treatment for best outcome and least risk, and suggest the use of genetic testing in clinical decision making.

II. STUDY OBJECTIVE(S); INCLUDING SPECIFIC AIMS AND/OR HYPOTHESES

The hypothesis, or idea being tested, is that as long as patients have a favorable CIS they can be successfully treated with IAT out to 24 hours. For patients with poor CIS, success rates will be relatively low, with no benefit provided by IAT. The long term objective is to:

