- a. Lengthen the time window of treatment for patients with fCIS from 6 hours to 24 hours. In doing so, we will offer useful treatment to patients who would otherwise be denied treatment under current standards.
- b. Encourage focusing on achieving good revascularization rather than limiting time during IAT for patients with fCIS.
- c. Improve the percentage of good outcomes in the treated population
- d. Save patients with pCIS from complications due to brain edema and intra-cranial hemorrhage that could potentially result from IAT
- e. Save the health care system the costs of futile treatment of patients with pCIS.

III. METHODS

A. Study Design:

Version: 6.0

The current study focuses on patients with acute ischemic stroke due to a blockage of the intracranial internal carotid artery or middle cerebral artery (M1). The study will be performed prospectively in up to 6 stroke centers. Akron General Medical Center is the primary institution for development of the study and data analysis for this multicenter trial. To participate in the study, all centers need to meet certain qualified requirements which include:

- One neurointerventionalist with 6 years' experience in performing IAT with multiple devices.
- Demonstrate coverage of the comprehensive stroke center 24 hours a day. The proposed study will be carried out over a period of 4 years from the initial approval date. Informed consent will be obtained for each patient, as described in section VIII. The study will be carried out in 2 phases (Figure 1).

Phase I will compare outcomes between treated patients with fCIS and pCIS. All eligible patients will be assessed by a full diagnostic cerebral angiogram with dye injection of all potential collaterals. DCA will be used to characterize the CIS. Treatment will be identical for both groups. All patients will be treated with the combination of IAT and the normal standard of care for a patient not receiving IAT (which may include IVT, but not always). The sample size will be set to have 60 patients complete the trial. Distribution of fCIS and pCIS patients will not be forced, but the option to balance groups may be employed if the percentage for one group reaches 70%.

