The population for the study will be patients with anterior circulation acute ischemic stroke due to blockage of the intracranial internal carotid artery or middle cerebral artery (M1) within 8 hours of onset of symptoms. Typically, IAT is only offered to patients up to 6 hours, with no treatment options directly targeting the clot available after that time. Occlusion of one of these vessels will be determined based on CT angiography, magnetic resonance angiography, or DCA. Only patients 18 or over will be considered for the study. Other inclusion criteria include a score of 8 or greater on the National Institute of Health Stroke Scale (NIHSS, see appendix). Exclusion criteria will include contra-indication for IAT found on initial CT, intracranial hemorrhage, stroke mimics (tumor, herpetic encephalitis, etc.), more than 1/3 hypodensity on non-enhanced head CT prior to intervention, ASPECT Score < 6, and pre-existing disability defined as mRS ≥ 2. Pregnant women will also be excluded.

[figure not shown]

Figure 1: Study design for Phase I

Version: 6.0 5

[figure not shown]

Figure 2: Study design for Phase II

C. Assessment of Resources

The multicenter study will be carried out at up to 6 stroke centers. Each center is expected to have approximately 1 patient per month eligible for the study. Enrollment of patients will be performed at the end of imaging at each institution. At Akron General Medical Center, consent will be obtained within the DCA imaging suite. Consent will be obtained by a person qualified by the local IRB other than the treating physician. At Akron General, consent will be acquired by one of two neurointerventional lab nurses. One of these two nurses is required to be present for treatment of each patient with acute ischemic stroke, regardless of participation in a study. These nurses are familiar with all aspects of the proposed treatment methods and typical outcomes. The nurses will perform documented training on methods for obtaining consent and maintaining confidentiality of data obtained from subjects enrolled in research projects.

D. Study Procedures

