Pre-operative condition and patients outcomes will be assessed using standardized and validated measures. The primary endpoint of a mRS score will be obtained at least 90 days following treatment and again at 1 year following treatment. NIHSS score will be obtained in the emergency room before the treatment, within 24 h of treatment, and before discharge. The person who will obtain the NIHSS will be certified to obtain it. Adequacy of revascularization will be assessed at the end of treatment by the treating physician according the modified thrombolysis in cerebral infarction (mTICI) scale (see Appendix). All of these measures are standards for care and trials of acute ischemic stroke. [8-10] All case report forms will be maintained by the primary investigator at the local site, and stored within locked cabinets. The personal identifying information on the case report forms will be deidentified and assigned a code before being transferred to Akron General Medical Center for transfer of the data to a de-identified database which will be used for analysis.

IV. DATA COLLECTION

Version: 6.0

A. How and what data will be collected

Data related to patient demographics, stroke risk factors, condition prior to treatment, time of treatment, and outcomes will be collected for each patient. Data on demographics will include sex, age, and race. Data on stroke risk factors will include history of hypertension, blood pressure, prior heart attack, arrhythmias, diabetes, glucose (sugar) level at admission, and obesity. Data on condition prior to treatment will include NIHSS score determined in the emergency room. Data on time of treatment will include time from symptoms to arrival at emergency room, time to start of DCA, and time to end of the procedure. Data on outcomes will include mRS at 3 months, mRS at 1 year, NIHSS score within 24 hours and at discharge, and complications brain edema and intra-cranial hemorrhage. Other parameters within these categories could be acquired as deemed necessary for analysis of the data.

V. DATA ANALYSIS

A. Sample Size Considerations

Phase I

A power analysis has been performed based on the previous retrospective analyses of the relationship between outcomes and the CIS for phase I. The sample size was calculated for the influence of the combination of CIS and revascularization on good outcomes (mRS \leq 2) based on the following assumptions.

- The percentage of patients with fCIS will be 60%

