- The percentage of patients with good revascularization will be 50%
- The rate of good outcomes for the combination of fCIS and good revascularization is assumed to be 70%
- The rate of good outcomes for the combination of fCIS and poor revascularization is assumed to be 20%
- The rate of good outcomes for the combination of pCIS and good revascularization is assumed to be 20%
- The rate of good outcomes for the combination of pCIS and poor revascularization is assumed to be 10%

The assumptions provide the following power analysis:

- $\alpha = 0.05$ for overall analysis and set to 0.025 for subgroup analysis comparing fCIS and good revascularization to all other groups due to multiple comparisons
- power = 0.90
- Needed Sample size = 54 patients
- An additional 6 patients completing the trial are budgeted due to risk of errors in estimated outcomes. An additional 15-20 patients are expected to be enrolled due to patients lost to the 90 day follow up and/or deviations from the protocol.

Phase II

Phase II will be an exploratory study evaluating the rates for good outcomes for patients with pCIS treated with IVT plus IAT vs. IVT (or other standard of care) only. The rate of good outcomes is expected to be approximately 13% for the IAT group with revascularization. The investigators have no prior data on expected rates of good outcomes for patients with pCIS treated with IVT only. The best possible outcome rate would be on

Version: 6.0

the order of 25% noted previously for untreated acute ischemic stroke. Due to the low levels of good outcomes, the investigators acknowledge the study will be underpowered to detect a difference between the two treatment groups for a total sample size of 30. Phase II will serve as a pilot study to initially establish estimates of rates of good outcomes for pCIS patients treated with IVT only for design of a larger prospective study.

Genetic Analysis

Genetic analysis will be performed based on the following:

- Genetic and expression analysis for the two groups based on their collateral score
- Adjust groups for cardiovascular/stroke risk factor presence and other known confounding conditions
- High density SNP array analysis will be performed for common and rare alleles
 against known collateral-related genes that have been identified in mice. These
 include human RABEP2 and its isoform RABEP1 and related gene pathways;
 VEGFA, FLK1 and their related gene pathways; NOTCH, DLL4, ADAM10,

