 ADAM17, CNX37 and their related gene pathways.
- Subgroup analysis will be performed for ethnicities.
- Taqman assays and/or exome sequencing of significantly associated SNPs and/or genes.
- Pending results, a future validation study will follow this discovery study by increasing the sample size.

B. Statistical Methodology

Data for the proposed study will be analyzed using comparison of proportions and multivariable logistic regression. Analysis of proportions based on Fisher exact tests will be used to compare rates of good outcomes between the fCIS and pCIS groups as the primary end point for phase I. The influence of successful revascularization on outcomes for patients with fCIS or pCIS will also be analyzed using Fisher exact tests as the secondary end point.

Binary and/or ordinal multiple logistic regression analyses will be used to evaluate the influence of multiple parameters on the likelihood of a good outcome. These parameters will include CIS, mTICI score, NIHSS score, time to revascularization, age, sex, history of diabetes mellitus, history of high blood pressure, history of coronary artery disease. The same analyses will be performed for phase II, instead focusing on the treatment groups rather than the CIS classification.

VI. DATA AND SAFETY MONITORING PLAN

A. Describe any provisions for monitoring the data for safety

A safety committee will monitor the data. The safety committee will be composed of at least 3 voting members. At least two members will be neurologists, neuroradiologists or neurointerventionalists with experience treating acute ischemic stroke who are not investigators at any of the sites. These members will not be affiliated with the institution of the principal investigator, any sub- investigator, or Akron General Medical Center. At least one member with a background in biostatistics who is not an investigator or affiliated with Akron General Medical Center will also be on the committee.

For phase I, the only deviations in normal standards of care are:

Version: 6.0

- 1- the extra few minutes for full DCA for some centers as opposed to injecting only the occluded vessel
- 2- Adding IAT to treatment of patients seen between 6 and 24 hours of onset of symptoms.

The safety committee will be looking at known potential complications for IAT in both fCIS and pCIS groups. These include:

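### Phase I tests CIS pooled over all treatment times, so no planned analysis estimates outcome in late-treated fCIS patients, and the only time covariate is undefined

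*Combined protocol and SAP*

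**What the plan says.** Section II gives the idea being tested: "as long as patients have a favorable CIS they can be successfully treated with IAT out to 24 hours". Objective a is "Lengthen the time window of treatment for patients with fCIS from 6 hours to 24 hours". Objective b is to put good revascularization ahead of limiting time during the procedure in fCIS patients. Section VIII.D offers treatment beyond 6 hours as the Phase I benefit.

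Section V.B plans three things for Phase I:

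- a Fisher exact test of good outcome, fCIS against pCIS (primary);
- Fisher exact tests of the influence of revascularization in fCIS and pCIS patients (secondary);
- binary and/or ordinal logistic regression: "These parameters will include CIS, mTICI score, NIHSS score, time to revascularization, age, sex", followed by three medical-history items, nine parameters in all.

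Time to revascularization is the only time parameter. The times that Section IV.A lists for collection are "time from symptoms to arrival at emergency room, time to start of DCA, and time to end of the procedure". Section V.A assumes: "The percentage of patients with good revascularization will be 50" (percent).

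On the window itself, Section III.B describes the population as presenting "within 8 hours of onset of symptoms", while Section VI.A describes Phase I as "Adding IAT to treatment of patients seen between 6 and 24 hours of onset of symptoms".

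**The concern.** The hypothesis is about time within the fCIS group: whether late treatment still works when the CIS is favorable. The primary test asks whether fCIS patients do better than pCIS patients, averaged over whatever mix of treatment times is enrolled. The second question can be answered clearly while the first stays open.

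The regression does not close the gap as listed. With CIS and time entered as separate terms, the model imposes one time effect on both CIS groups, and that sameness is what the hypothesis disputes. The time variable also needs a definition. A patient who is never revascularized has no time to revascularization, and the protocol says neither what value such a patient receives nor how the variable is derived from the times collected.

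At stake is the conclusion on the treatment window. A significant pooled result could be read as support for extending it when no late-fCIS figure has been specified or reported. Phase II cannot supply the figure, because it enrolls only pCIS patients.

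**Working it through.** **Inputs.** Section III.A: "The sample size will be set to have 60 patients complete the trial". Section V.A: 60% fCIS; 50% good revascularization; good-outcome rates of 70% (fCIS, good revascularization), 20% (fCIS, poor), 20% (pCIS, good) and 10% (pCIS, poor); alpha 0.025 for fCIS with good revascularization against all others; power 0.90; needed N = 54. Section V.B: nine covariates. The share of fCIS patients treated after 6 hours is not given; I assume 20-50%.

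**1. The plan's own N.** Taking CIS and revascularization as independent, the four cells hold 30%, 30%, 20% and 20% of patients. The rate outside the fCIS/good-revascularization cell is (0.30×20% + 0.20×20% + 0.20×10%)/0.70 = 17.14%. I use the pooled-variance formula for two proportions,

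n₁ = [z(1−α/2)·√(p̄(1−p̄)(1+1/k)) + z(power)·√(p₁(1−p₁) + p₂(1−p₂)/k)]² / (p₁−p₂)²,

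with p₁ = 0.70, p₂ = 0.1714, k = 0.7/0.3, p̄ = 0.33 and two-sided α = 0.025. This gives n₁ = 13.3, and 15.9 after continuity correction. Rounding up gives 16 + 38 = 54, the plan's figure. Sidedness and continuity correction are not stated in the plan; a four-group chi-square test (3 df, alpha 0.05) gives 53. Neither calculation contains a time element.

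**2. What the primary test can show.** Expected rates are 0.5×70% + 0.5×20% = 45% for fCIS and 0.5×20% + 0.5×10% = 15% for pCIS. With 0.60×60 = 36 fCIS and 24 pCIS patients, expected good outcomes are 16.2 and 3.6, rounded to 16 and 4. Fisher exact, 16/36 vs 4/24: p = 0.029. Now assume 20% of fCIS patients are late, so 7 late and 29 early. If all 16 good outcomes fall in early patients (16/29 early, 0/7 late), the table and the p-value are unchanged. The late rate would then be 0/7, with exact upper limit 1 − 0.025^(1/7) = 41%. The primary result is silent on that difference.

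**3. Precision of a late-fCIS estimate.** Exact (Clopper-Pearson) 95% CIs near the implied 45%:

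| Assumed late share of 36 | Late fCIS | Good outcomes | 95% CI |
|---|---|---|---|
| 20% | 7 | 3 | 10-82% |
| 30% | 11 | 5 | 17-77% |
| 50% | 18 | 8 | 22-69% |

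A formal early-versus-late test within fCIS would have little power. For 45% vs 25%, two-sided 0.05, Fisher power is 9% (29 vs 7), 14% (25 vs 11) and 16% (18 vs 18).

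**4. The time covariate.** Patients without good revascularization: 0.50×60 = 30. Expected good outcomes in all 60: 16.2 + 3.6 = 19.8, or 19.8/9 = 2.2 per covariate. If those 30 had no value and the fit were complete-case, the remaining 30 (18 fCIS, 12 pCIS) would have 18×0.70 + 12×0.20 = 15 good outcomes, or 15/9 = 1.7 per covariate. Both conditions are needed for that loss, and the protocol states neither.

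**The case against.** Several points against the concern have force.

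- **A reader might infer that half the patients will drop out of the regression.** The documents do not support this. The 50% is the share without *good* revascularization. The mTICI scale in the appendix has partial grades (1 and 2a), so some of these patients have partial reperfusion. No section prescribes complete-case fitting. Section IV.A also collects time to the end of the procedure and allows other parameters to be acquired. If end of procedure is what was meant, nobody is lost. The criticism that remains is an undefined covariate.
- **Objectives a to e are introduced as long-term, and Phase I is described as an fCIS-pCIS comparison, which the primary test performs.** This is true, and the test is valid for that question. But the 24-hour statement is given as the hypothesis being tested, not only as a long-term aim.
- **Section V.B does not exclude an interaction.** Also true. It does not name one either, so the answer is left to choices made after the data are seen.
- **One replacement time variable would not serve both objectives.** Onset-to-DCA start ends before clot removal, so it says nothing about time during the procedure (objective b). This stands, and the fix uses two times.
- **The subgroup is small, and an added model term would overfit.** This stands. It argues for a pre-specified estimate with its interval and against a further test.
- **If the 8-hour limit applies, a stratum over 6 hours says little about 24 hours.** This stands, and it limits what the estimate can support.

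**Conclusion.** The gap is real: Section V.B contains no estimate of outcome in late-treated fCIS patients, and no other section supplies one. A significant pooled result would be compatible with any late-fCIS outcome, as the 16/36 vs 4/24 example shows. It would be wrong to conclude that the primary test is invalid or that N = 54 is miscalculated; the figure reproduces.

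The covariate problem is secondary. Time to revascularization is undefined and not among the listed times. Up to about 30 of 60 patients could be affected, but they would be lost only if no value is assigned and the fit is complete-case.

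Precision rests on the plan's 60% fCIS share and implied 45% rate, and on my assumed late share of 20-50%. The 70% rate should not be used for this estimate, because the plan assumes it only for fCIS with good revascularization. On those assumptions the interval is no narrower than about 22-69%. Phase I has no untreated arm, so the estimate describes outcome in treated patients and does not show benefit over no treatment.

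How far the estimate reaches depends on the 8-hour wording (Section III.B) and the 24-hour wording (Sections II, VI.A and VIII.D), which contradict each other. A late stratum exists under either, but its range differs greatly.

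**What to change.** In Section V.B:

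1. Pre-specify, as the estimate for the time-window hypothesis, the good-outcome rate (mRS ≤ 2) with exact 95% CI in fCIS patients with onset-to-DCA start over 6 hours, beside the same figure for 6 hours or less. State that any claim about the window rests on this estimate, only over the range of times actually enrolled, and not on the pooled fCIS-pCIS test.
2. Replace time to revascularization with collected times that exist for every treated patient: onset-to-DCA start for the window question, and time to end of procedure (or DCA start to end of procedure) for objective b. State in Section IV.A that symptom onset is the origin for the first.
3. Treat any CIS-by-time term as exploratory, fitted outside the nine-covariate model and reported as an estimate with CI, because only about 20 good outcomes are expected.

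Separately, reconcile the 8-hour and 24-hour passages, and describe the late stratum to match.

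Cost: changes of wording and one extra table from data already collected. The downside is that the wide interval will limit what can be said about the time window.

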D. The investigators have retrospectively examined the CIS for patients previously treated with IAT for this type of stroke [13-15], initially via large case series analyses and subsequently by blinded application of the CIS to patients in three major prospective randomized placebo- controlled clinical trials. [9-11] The previous studies indicated that patients graded as having a fCIS, indicating good peripheral blood flow, typically have good clinical outcomes following successful revascularization. A good outcome is defined as a slight disability and able to carry out daily activities or better. Good outcome rates have been on the order of 70-90% for patients with a favorable CIS and good revascularization. This proportion of good outcomes far exceeds any published rate of good outcomes using all other peer- review published patient selection methodologies to date. For patients with a pCIS, the maximum rate of good outcomes has been 13% despite good and timely revascularization, which is actually well below the success rate of approximately 20% for patients who are left untreated, without even tPA [7]. These results raise the question if we are not only not helping the patients with pCIS but also actually harming them. Clinical trials focused on IAT have had mixed results, with some trials showing no benefits compared to IVT with tPA alone [5, 8], and more recent trials showing superiority of the IAT plus IVT over IVT alone [3,13-14,16]. The absolute rates

Version: 6.0

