In phase II, after confirming the hypothesis that patients with pCIS tend to have poor outcomes as compared to the natural history of the disease, only patients with pCIS will be enrolled. 30 patients will be randomized into treatment including IAT or without IAT plus standard of care based on a simple 1:1 randomization. All otherwise IV tPA eligible patients will be treated with IVT using tPA regardless of the assigned group since this represents current standard of care. Based on previous studies, the results from Phase I should show poor results for pCIS patients, on the order of 15% good outcomes, below the published good outcomes for patients receiving no treatment. This phase will provide preliminary data to determine if IAT provides any benefit in these patients, or is even potentially harmful, which no other clinical trial to date of IAT has formally hypothesized or tested as plausible. Due to the low rate of success the investigators realize this phase will be underpowered to definitively show differences between two groups, but the phase will provide preliminary safety pilot data on a topic not studied to date to develop plans for a larger and adequately powered study.

All eligible patients participating in both phase I and phase II will be given the option to donate an additional 8.5 ml blood sample for genetic testing of the *Dce1* gene. Blood samples will be collected in Paxgene DNA tubes. Collection of this sample will occur during regularly scheduled blood work within 48-60 hours of admission. Akron General will store all samples until all patients are enrolled after which the samples will be sent to a biospecimen processing facility to identify polymorphisms of the *Dce1* gene. Results obtained from the genetic testing will be analyzed in conjunction with data from phase I and II.

The primary measure of outcome will be the same for both phases. The outcomes will be measured based on the modified Rankin Scale (see appendix) at least 3 months and again at 1 year following treatment. Patients will be graded according to this scale by an experienced

Version: 6.0

neurologist or other mRS scale certified health care provider not involved in the treatment and blinded to the treatment for each patient.

B. Study Population:

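### Phase I cannot confirm that IAT-treated pCIS patients do poorly against the natural history, because the untreated rates cited are not shown to be pCIS rates

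*Combined protocol and SAP*

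**What the plan says.** Section III.A (Study Design) has Phase II start "after confirming the hypothesis that patients with pCIS tend to have poor outcomes as compared to the natural history of the disease". It expects Phase I to show, for pCIS patients, a result "on the order of 15% good outcomes, below the published good outcomes for patients receiving no treatment".

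Two untreated rates serve as the yardstick:
- Section I.D reports earlier data: "For patients with a pCIS, the maximum rate of good outcomes has been 13% despite good and timely revascularization". It calls this "well below the success rate of approximately 20% for patients who are left untreated, without even tPA" and adds: "These results raise the question if we are not only not helping the patients with pCIS but also actually harming them".
- Section V.A (Phase II) takes as the best achievable rate for pCIS patients without IAT a figure on "the order of 25% noted previously for untreated acute ischemic stroke". Just before that it concedes: "The investigators have no prior data on expected rates of good outcomes for patients with pCIS treated with IVT only".

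Neither figure is described as coming from pCIS patients. Section III.A gives IAT to every Phase I patient. Section V.B makes the Phase I primary analysis a Fisher exact test of fCIS against pCIS, and specifies no analysis against natural history.

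The condition for starting Phase II is described in two other ways. Section VI.A gives good outcomes above expectation in treated pCIS patients as the main reason not to launch. Section VIII.B refers to a treated pCIS rate under 15%.

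**The concern.** Whether IAT fails or harms pCIS patients depends on what the same kind of patient would have done without it. Phase I does not observe that, and section V.A says no such data exist for pCIS patients given IVT only. The published untreated rates stand in for it. If CIS is prognostic, as the protocol holds, an untreated rate from a population that includes fCIS patients would overstate the untreated pCIS rate. By calling 25% the best that could be expected, section V.A treats it as a ceiling, while section III.A uses the published untreated rate as a comparator.

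At stake is how Phase I is read. A low treated pCIS rate is evidence about prognosis under IAT. Presented as confirmation against natural history, it becomes evidence of futility or harm. That reading would sit behind the randomization of pCIS patients to no IAT, and behind the long-term objectives in section II of sparing pCIS patients IAT complications and the health system their cost. Phase II is unlikely to correct a misreading, since the protocol itself calls it underpowered.

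**Working it through.** **Inputs.** From V.A: 60% fCIS (so 40% pCIS), 50% good revascularization, and good-outcome rates of 70% (fCIS, good revascularization), 20% (fCIS, poor), 20% (pCIS, good) and 10% (pCIS, poor). From III.A: 60 Phase I completers and 30 Phase II patients randomized 1:1. Untreated benchmarks: 20% (I.D) and 25% (V.A). Treated-to-control ratio in positive IAT trials: about 1.7 (I.D).

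**The plan's own figures.** Treated pCIS rate = 0.5 × 20% + 0.5 × 10% = 15%, which matches III.A. The Phase I sample size of 54 also reproduces. For fCIS with good revascularization (70%) against all others (17.1%), at two-sided alpha 0.025, 90% power and with continuity correction, n = 16 + 38 = 54. Neither figure is in dispute.

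**CIS is prognostic in the plan's rates.** With poor revascularization, fCIS is 20% and pCIS 10%, a ratio of 2.0. These patients still had the procedure, so this is only a proxy for untreated outcome.

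**What a treated 15% means.** Let f and q be the untreated fCIS and pCIS rates, and assume the benchmark population has the plan's 60/40 mix. Then B = 0.6f + 0.4q. A treated rate t is a benefit when q < t. At break-even q = t, so f = (B − 0.4t)/0.6 and the ratio is f/t.

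| Benchmark B | Treated t | Break-even f | Break-even f/q |
|---|---|---|---|
| 20% | 15% | (20 − 6)/0.6 = 23.3% | 1.56 |
| 25% | 15% | (25 − 6)/0.6 = 31.7% | 2.11 |
| 20% | 13% | (20 − 5.2)/0.6 = 24.7% | 1.90 |
| 25% | 13% | (25 − 5.2)/0.6 = 33.0% | 2.54 |

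Above the break-even ratio the treated rate is a benefit; below it, a deficit. The proxy ratio of 2.0 falls between 1.56 and 2.11, so for t = 15% the sign depends on the benchmark. With q = B/(0.6 × 2 + 0.4) = B/1.6:
- B = 20% gives q = 12.5%, so treated 15% is 2.5 points better.
- B = 25% gives q = 15.6%, so treated 15% is 0.6 points worse.

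Against the benchmarks themselves, 15% looks 5 and 10 points worse.

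**Precision.** 40% of 60 is 24 pCIS patients. An observed 3/24 (12.5%) has an exact 95% CI of 2.7% to 32.4%. If the true treated rate is 15%, the observed rate falls below 20% (at most 4 of 24) with probability 71%, and below 25% (at most 5 of 24) with probability 86%.

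**Phase II as a corrective.** With 15 per arm, Fisher exact power is about 1.5% for 15% against 10%, and about 6% for 13% against 25%.

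**The case against.** The case on the other side has five parts, and much of it stands.

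- **No analysis uses the benchmark.** Section V.B tests fCIS against pCIS, and sections VI.A and VIII.B describe the Phase II launch without natural history. This is true. The problem lies in the confirmation claimed in III.A and the reading in I.D, not in a planned test.
- **The design already leaves the question to randomization.** Section III.A says Phase II will give preliminary data on benefit or harm, I.D only raises harm as a question, and the lack of power is admitted. This softens the consequence. It does not make the confirming step valid.
- **The scenarios disagree in direction.** With a 25% benchmark and untreated fCIS at 30% (assumption), untreated pCIS is (25 − 18)/0.4 = 17.5%, so a treated 13-15% really is lower. With a 20% benchmark and untreated fCIS also 20%, untreated pCIS is 20% and the comparison is fair. This stands.
- **The comparison carries some information.** A reader might infer that a low Phase I pCIS rate is equally likely whatever IAT does. That holds only if the treated rate is fixed. With untreated pCIS at 12.5% and 24 patients, the chance of observing less than 20% is about 40% under a 1.7-fold benefit (true rate 21.3%), and about 96% if IAT lowers the rate to 8% (assumption).
- **The benchmark population is not described.** A reader might take it as known to be unselected stroke. The documents show only that the patients were untreated and do not say they were pCIS. The 60/40 mix is an assumption.

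**Conclusion.** The point holds in limited form. Phase I has no untreated pCIS patients, and the published rates are not shown to be pCIS rates. A treated pCIS rate of 15% against 20-25% therefore cannot separate benefit, no effect and harm. On the 60/40 assumption it is a benefit only if untreated fCIS patients do more than 1.56 times (20%) or 2.11 times (25%) as well as untreated pCIS patients. Those untreated rates are unknown, and the interval from about 24 patients is wide enough to include both benchmarks.

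Two stronger readings are not supported. The documents do not show that IAT benefits pCIS patients, or that the benchmark comparison must mislead: some plausible inputs make it fair or make the deficit real. Nor do they say that Phase I alone will establish futility or harm. What fails is the claim of confirmation against natural history.

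**What to change.** - **Section III.A:** replace the natural-history confirmation with a descriptive statement. The Phase I pCIS good-outcome rate is reported with an exact 95% CI and interpreted as prognostic only, that is, fCIS against pCIS under IAT.
- **Sections III.A and V.B:** state that no conclusion of futility or harm from IAT in pCIS will be drawn from published untreated rates. Only the randomized Phase II contrast, reported with a confidence interval and as a pilot, bears on benefit or harm.
- **Sections I.D and V.A:** label the 20% and 25% figures as not pCIS-specific.
- **Reconciliation by the sponsor:** the two benchmark values (20% and 25%), and the differing descriptions of the Phase II launch condition in III.A, VI.A and VIII.B. This point does not propose which launch condition should apply.

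The cost is protocol wording. Sample size, procedures and the planned Fisher tests are unchanged. The downside is that Phase I can no longer be presented as evidence that IAT is futile or harmful in pCIS.
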